## 6. GENERAL ANALYSIS DEFINITIONS

### 6.1 TREATMENT(S)

For details on the treatment regimen, assignment of treatment groups, and the selection of doses, refer to Section 4 of the CTP. Below in Table 6.1:1 are the descriptions of the short and long names of the treatments. Next, are the definitions of the study phases for the analysis periods (Table 6.1:2).

Table 6.1: 1 Treatment descriptions

| Long Name            | Short Name |
|----------------------|------------|
| Placebo              | Placebo    |
| BI 1358894 5 mg qd   | BI 5 mg    |
| BI 1358894 25 mg qd  | BI 25 mg   |
| BI 1358894 75 mg qd  | BI 75 mg   |
| BI 1358894 125 mg qd | BI 125 mg  |

Table 6.1: 2 Study analysis phases\*

| Study analysis phase                        | Description                    | Start Date (included)                               | End Date (included)                                |
|---|--------------------------------|---|--|
| Screening phase                             | Screening (prior to treatment) | Date of informed consent                            | Date of first treatment administration minus 1 day |
| Treatment phase and residual effects period | On-treatment period            | Date of first treatment administration              | Date of last treatment administration + REP        |
| Follow-up phase                             | Off-treatment period           | Date of last treatment administration + REP + 1 day | Date of last CTP visit                             |

\* The defined treatment periods are the same for all treatment groups.

REP is the residual effect period which is defined as 28 days after the last dose of trial treatment for safety, and 7 days after last dose for efficacy

Dates are defined individually per patient. If more than one date is associated with a specific visit, measurements associated with a specific date are assigned to a study analysis phase according to the rules specified in the table. An analysis phase will not extend beyond the start date of the following phase.

### 6.2 IMPORTANT PROTOCOL DEVIATIONS

Data discrepancies and deviations from the CTP will be identified for all patients in the database (i.e., randomized patients). Consistency check listings (i.e., identification of violations of time windows) and a list of CTP deviations will be provided to be discussed at the Report planning meeting (RPM)/Database lock meeting (DBLM)/Medical Quality Review Meeting (MQRM). At these meetings, it will be decided whether a discrepant data value can

be used in analyses and/or whether it must be queried in the clinical database. Each CTP deviation must be assessed to determine whether it is an important Protocol Deviation (iPD). For definition of iPDs, and for the process of identification of these, refer to the current BI reference document "Identify and Manage Important Protocol Deviations (iPD)" (3).

Generally, a protocol deviation is considered as an iPD if it affects the rights or safety of the study subjects, or if it can potentially influence the primary outcome measurement(s) in a non-negligible way. If any iPDs are identified, they are to be summarized into categories and will be captured in the RPM/DBLM/MQRM minutes via an accompanying DV domain specifications Excel spreadsheet (4). If the data presents additional iPDs (e.g., based on monitor visits to the sites), then the DV domain specifications will be supplemented accordingly at TOMs or RPMs or through team review of the manual PD log.

The decision whether a patient will be excluded from the analysis will be made at the final RPM prior to Database Lock (DBL). The documentation of the iPD categories and how to handle iPDs in the analysis are listed in the DV domain specifications and stored within the Trial Master File (TMF) in Electronic Document Management System (EDMS). iPDs will be summarized and listed for the treated set.

### **6.3 SUBJECT SETS ANALYSED**

The following analysis sets are defined for this trial:

- Screened Set (SS): consists of all subjects who signed informed consent.
- Treated Set (TS): consists of all subjects that have been randomized and that received at least one administration of study drug. The TS will be the main analysis set for the evaluation of safety. Subjects are analysed according to the actual received treatment.
- Full analysis set (FAS): consists of all subjects in TS that have a baseline and at least one evaluable post-baseline measurement for the primary endpoint. This is the main analysis set for the evaluation of efficacy data.
- Per protocol set (PPS): This is a subset of FAS, for subjects with adequate protocol compliance. It consists of all subjects in FAS without any important protocol deviations that impact efficacy assessments.
- Adherent set (AS): consists of all subjects in FAS that are at least 60% overall AiCure adherent to study medication. See [Section 7.3.2](#) for further information.

- 

Table 6.3: 1 Subjects' sets analyzed

| Class of endpoint  | Subject set |    |     |     |   |    |
|--|-------------|----|-----|-----|---|----|
|  | TS          | SS | FAS | PPS | █ | AS |
| Primary and secondary endpoints, compliance                  |             |    | X   | X*  |   |    |
| Further endpoints (except PK)                                |             |    | X   |     |   |    |
| Disposition  |             | X  |     |     |   |    |
| █  |             |    |     |     | █ |    |
| Safety variables and iPDs                                    | X           |    |     |     |   |    |
| Demographics, baseline variables, exposure                   |             |    | X   | (X) |   |    |
| Primary endpoint adjusted for overall study AiCure adherence |             |    |     |     |   | X  |

\* If the percentage of subjects in FAS with iPD that lead to the exclusion from the PPS is > 10%, then sensitivity analysis of the primary and secondary efficacy endpoints using PPS may be conducted.

(X) An additional PPS presentation of the demographic/baseline endpoints may be provided in the End of Text (EoT) section, if there are a non-negligible number of subjects that were treated, but without any post randomization data for the primary endpoint.

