## **7.3 TREATMENT COMPLIANCE**

### **7.3.1 CRF Compliance**

Only descriptive statistics are planned for this section of the report. Treatment compliance is calculated at Week 1, 2, 4, 6, 8, 10 and 12(EOT) based on the CTP's flow chart.

Treatment Compliance = (number of tablets taken during a period) / (number of tablets that should have been taken during a period) \* 100.

The cumulative treatment compliance during the entire treatment period is derived using the following examples:

For completers: if a subject's observed treatment compliance rates are 80%, 81%, 82%, 83%, 84%, 85%, 86% at Weeks 1, 2, 4, 6, 8, 10 and 12, then the cumulative treatment compliance percent =  $(.80*1 + .81*1 + .82*2 + .83*2 + .84*2 + .85*2 + .86*2)/12*100 = 83.42\%$ .

For early discontinued subject: if a subject's observed treatment compliance rates are 80% at Week 1, 81% at Week 2, 82% at Week 4, 50% at eEOT, then the cumulative treatment compliance rate =  $(0.80*1 + 0.81*1 + 0.82*2 + 0.5*((eEOT\ date - drug\ start\ date + 1)/7 - 4))/((eEOT\ date - drug\ start\ date + 1)/7) * 100\% = 74.3\%$  if the quantity (eEOT date – drug start date + 1) is assumed to be 36 days.

If at a particular visit a participant did not return the trial drug kits, then the compliance at that visit is zero.

Treatment compliance will be summarised overall and by visit for the treated set (FAS) using descriptive statistics (N, mean, SD, minimum, median, maximum). The number and percentage of patients with the following overall compliance categories will be presented

using descriptive statistics (N, mean, SD, minimum, median, maximum). The number and percentage of patients with the following overall compliance categories will be presented:

- "<80%",
- "80% to <100%",
- "≥100%",
- missing.

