## **7.7 EXTENT OF EXPOSURE**

Extent of exposure will be calculated as the difference between last intake of study drug and the first administration of the study drug plus one day. Descriptive statistics will be provided for number of days of exposure for each treatment arm. Also, cumulative exposure of number and percentage (N, %) of subjects will also be displayed as “< 1 week”, “1 to < 2 weeks”, “2 to <3 weeks”, “3 to <4 weeks”, “4 to <6 weeks”, “6 to <8 weeks”, “8 to <10 weeks”, “10 to <12 weeks”, “12 weeks”, “>12 weeks”, or “missing”.

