## **7.8 SAFETY ANALYSIS**

All safety analyses will be performed on the treated set. AEs will be coded based on the most current version of MedDRA. Analysis will be performed as defined in Section 7.2.5 of the CTP.

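### Exposure is summarised on the FAS while adverse events use the treated set, so treated patients with no later ZAN-BPD rating are missing from the exposure summary

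*SAP*

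**What the plan says.** **Analysis sets.** SAP 6.3 defines the TS as randomised patients with at least one administration of study drug, analysed by the treatment actually received: "The TS will be the main analysis set for the evaluation of safety". The FAS is narrower and "consists of all subjects in TS that have a baseline and at least one evaluable post-baseline measurement for the primary endpoint".

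**Assignment of outputs.** In SAP Table 6.3:1 the row "Demographics, baseline variables, exposure" is marked under the FAS, with an optional per protocol set (PPS) display and nothing under the TS. The row "Safety variables and iPDs" is marked under the TS. SAP 7.8 agrees with the latter: "All safety analyses will be performed on the treated set".

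**Exposure section.** SAP 7.7 says "Descriptive statistics will be provided for number of days of exposure for each treatment arm" and plans a categorical display whose shortest row is under one week. It names no analysis set, and it stands outside the safety section, 7.8.

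**Compliance.** SAP 7.3.1 says "Treatment compliance will be summarised overall and by visit for the treated set (FAS", with the FAS in the parenthesis as though the two sets were one. Table 6.3:1 puts compliance on the FAS.

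**The concern.** Exposure by dose is read next to the AE tables: how many patients had how much drug, and for how long, when the events were counted. The two displays should describe the same patients.

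Here they need not, and the difference is not random. The FAS leaves out treated patients according to whether an efficacy rating followed dosing. Those without one are mainly patients who left soon after the first dose, so their exposures are short. If one dose were poorly tolerated early, its arm would lose the most patients from the short-exposure rows. The protocol says the trial is meant to support dose selection, so that is where a reader would want the exposure table to be complete.

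**Working it through.** The SAP states no figure on this point, so the check is a comparison of sets, followed by an illustration of size.

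**Step 1: who is in one set but not the other.** The FAS is a subset of the TS by definition. TS minus FAS is the treated patients with no baseline or no evaluable post-baseline ZAN-BPD. The protocol flow chart requires a ZAN-BPD before randomisation, so the missing-baseline route should be nearly empty. The missing post-baseline rating is what matters.

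**Step 2: which set governs exposure.** SAP 7.7 is silent, so Table 6.3:1 decides, and it says FAS. The column reading is supported elsewhere: SAP 6.2 also puts important protocol deviations on the TS, and the adherence row falls under the adherent set, as the text of 6.3 says.

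**Step 3: does a footnote repair it.** The (X) footnote to this row recognises treated patients without post-randomisation primary-endpoint data. Its remedy is a PPS display of demographic and baseline data. The PPS is a subset of the FAS, so it cannot contain these patients, and the footnote does not mention exposure.

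**Step 4: where the gap comes from.** Protocol 7.2.1 defines the FAS by one dose and a baseline, which is almost the TS. It leaves full specifications to the SAP, so adding a post-baseline requirement was permitted. That addition is what separates exposure from the AE tables, and SAP section 4 does not list it among the changes.

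**Step 5: size.** The documents do not give the number of treated patients without a later rating. Take 1%, 3% and 5% as assumed fractions f, and treat all 355 planned patients (119:47:47:47:95) as dosed. Number missing = f × n.

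| f | All 355 | 47-patient arm | 125 mg (95) | Placebo (119) |
|---|---|---|---|---|
| 1% | 3.6 | 0.5 | 1.0 | 1.2 |
| 3% | 10.7 | 1.4 | 2.9 | 3.6 |
| 5% | 17.8 | 2.4 | 4.8 | 6.0 |

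For mean exposure, assume 75 days in retained patients and 3 days in those left out. TS mean = (1 − f) × 75 + f × 3:

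- 1%: 74.25 + 0.03 = 74.3 days
- 3%: 72.75 + 0.09 = 72.8 days
- 5%: 71.25 + 0.15 = 71.4 days

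The FAS mean would be 75 days, an overstatement of 0.7, 2.2 and 3.6 days respectively. The shift in the mean is small. The patients left out belong mainly in the shortest rows, where counts are low and each patient matters more.

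**The case against.** The strongest reply is that little is lost, and most of it stands.

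- **Stopping in week 1 does not by itself remove a patient from the FAS.** A reader might infer that the shortest exposures disappear and the under-one-week row is empty. The documents do not support that. The protocol flow chart schedules a ZAN-BPD at the early end-of-treatment visit, to be held as soon as possible after stopping. Protocol 6.2.3 asks patients who stop to continue visits, or at least to attend Visit 8 or 9. SAP Table 6.7:1 opens the Visit 3 window on Day 2. The FAS definition does not say the rating must be on treatment. A patient with three doses and an early-termination rating stays in both the FAS and that row.
- **The patients' exposure is not unrecorded.** A reader might infer that AEs would be reported in patients with no exposure data. Their first and last dosing dates are needed to assign AEs to the on-treatment period (SAP 6.1, 7.8.1), and SAP section 7 lists individual values for all subjects. They are missing from a summary, not from the data.
- **AE frequencies do not depend on the exposure table.** SAP 7.8.1 counts patients with AEs, and the visible text plans no exposure-adjusted rate. Nor do the documents show that every omitted patient had an AE; these patients are in the denominator, not necessarily the numerator.
- **The compliance wording has an answer.** Table 6.3:1 resolves it as FAS. Changing only the phrase in 7.3.1 to the treated set would create a new contradiction.

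None of this removes the core: the two denominators differ whenever a treated patient has no later rating, and the SAP has no display that corrects for it.

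**Conclusion.** The point holds as a minor inconsistency. Followed as written, the SAP summarises exposure in a set that leaves out treated patients with no later ZAN-BPD rating, and counts those same patients in the AE tables. The under-one-week row is depleted rather than necessarily emptied, and mean exposure is slightly too high.

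The size is about 4-18 patients overall and 0.5-2.4 per 47-patient arm. This rests on the assumed 1-5%, for which the documents give no basis, and on all 355 patients being dosed. The shift in the mean rests further on the assumed 75 and 3 days. If every treated patient has a rating, the same patients appear in both sets.

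No AE percentage and no efficacy result changes, given that SAP 7.8 and the safety row of Table 6.3:1 govern the AE analyses.

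**What to change.** 1. In SAP Table 6.3:1, split the row that combines demographics, baseline variables and exposure. Assign exposure to the TS, grouped by actual treatment as for AEs. Demographics and baseline variables can stay on the FAS.
2. In SAP 7.7, name the TS as the set for the exposure summaries.
3. Separately, make SAP 7.3.1 and the compliance row of Table 6.3:1 name one set. If the FAS is kept, delete the reference to the treated set in 7.3.1. If the TS is chosen, change both places.

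The cost is a split table row, a sentence in 7.7 and a consistent wording for compliance. No data are added and no efficacy analysis is touched.

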## **6.5 POOLING OF CENTERS**

All subjects from all centers will be pooled for the statistical analysis of efficacy. The effect of region on the primary and selected secondary efficacy endpoints will also be investigated as described in [Section 6.4](#). Therefore, this section is not applicable because center/country is not included in the statistical model.

## **6.6 HANDLING OF MISSING DATA AND OUTLIERS**

Missing data are not explicitly imputed and remain missing for all main analyses. All but one of the CTP-defined primary and secondary efficacy endpoints are continuous. Therefore, for these efficacy endpoints which are continuous in nature, the use of a restricted maximum likelihood (REML)-based mixed model repeated measures (MMRM) approach will ensure that missing data are handled implicitly via a missing at random assumption (MAR) by the statistical model. For the binary efficacy endpoint of ZAN-BPD response, missing data will not be imputed.

Missing or incomplete AE dates are imputed according to BI standards (see “Handling of missing and incomplete AE dates”) [\(5\)](#). Missing data and outliers of PK data are handled according to [\(6\)](#).

## **6.7 BASELINE, TIME WINDOWS, AND CALCULATED VISITS**

Baseline is defined as the last observation at, or prior to Visit 2. Hence, if a subject is randomized at Visit 2, but does not start trial medication until a future visit (e.g., Visit 4), then his/her baseline is the latest assessment performed at Visit 2. However, for laboratory safety measurements, the last value prior to the first drug administration will be considered as the baseline value.

Planned and actual test days are included in the analysis data sets and are calculated relative to the beginning of treatment as indicated in [Table 6.7: 1](#) below.

For efficacy measurements, only one observation per time window will be selected for statistical analysis –the first one in the corresponding time window. If there are two observations which have the same difference in days to the planned day, or if there are two observations on the same day, the first value will be selected. If an observation is available on the last day of treatment, this observation will be preferably selected over any later observation that is still within the time window. Assignment of efficacy observations to visits based on time windows will be based on the non-imputed (observed) data. Repeated and unscheduled efficacy measurements will be assigned to the nominal visits according to the time windows described in [Table 6.7: 1](#).

For safety measurements, data collected at all visits will be used. For repeated and unscheduled safety measurements for the same visit on treatment, the worst of these will be selected for analysis. In the case for which there is no standard reference direction for the safety parameter, the average of all values for the same visit will be used for analysis.

Table 6.7: 1 Planned and actual study days

| Visit        | Relative to treatment start           |   |
|--------------|---------------------------------------|---|
|              | Planned test day                      | Actual test day   |
| 2            | 1                                     | Day 1   |
| 3            | 8                                     | Day 2 – Day 12  |
| 4            | 15                                    | Day 13 – Day 19   |
| 4A           | 22                                    | Day 20 – Day 26   |
| 5            | 29                                    | Day 27 – Day 33   |
| 5A           | 36                                    | Day 34 – Day 40   |
| 6            | 43                                    | Day 41 – Day 47   |
| 6A           | 50                                    | Day 48 – Day 54   |
| 7            | 57                                    | Day 55 – Day 61   |
| 7A           | 64                                    | Day 62 – Day 68   |
| 8            | 71                                    | Day 69 – Day 75   |
| 8A           | 78                                    | Day 76 – Day 82   |
| 9 / EOT      | 85 (for completed subjects)           | Day 83 – treatment stop date (stopdt) + 7 days  |
| eEOT         | N/A (for early discontinued subjects) | Date of the last administration of trial medication + 7 days (for early discontinued subjects).

The number of days will be assigned to the visit. Thus, if days to eEOT is 56, it will be mapped to Visit 7. For those that early discontinue treatment but continue with the collection of efficacy data, those data points will be mapped to the later Visits as per the above Visit window. Hence, if this same subject collects ZAN-BPD at Day 74, it will be mapped to Visit 8. |
| FUP1         | stopdt + 8 days                       | (stopdt + 8 days) to (stopdt + 11 days)   |
| FUP2         | stopdt + 14 days                      | (stopdt + 12 days) to (stopdt + 25 days)  |
| End of Trial | stopdt + 28 days                      | (stopdt + 26 days) to stopdt + 30 days  |

- Days are counted relative to the day of randomization, which is defined as Day 1.
- stopdt stands for treatment stop date.

*There is no visit window mapping for C-SSRS given that it is collected nearly every week throughout the study.*

## **7. PLANNED ANALYSIS**

The format of the listings and tables will follow the BI guideline "Standards for Reporting of Clinical Trials and Project Summaries" ([7](#)).

The individual values of all subjects will be listed, sorted by dose group, subject number and visit. AE listings will be sorted by assigned treatment (see [Section 7.8.1](#) below for details). The listings will be contained in an Appendix of the CTR.

For End-Of-Text tables, the set of summary statistics is N / Mean / Standard Deviation (SD) / Min / Median/ Max. For tables that are provided for endpoints with some extreme data, median, quartiles and percentiles are preferred to mean, standard deviation, minimum and maximum. In general, means, medians, and percentiles are presented to one more decimal place than the raw data and SDs are presented to two more decimal places than the raw data. Minima and Maxima are presented to the same number of decimal places as the raw data.

Disposition of the patient population participating in the trial will be analyzed by treatment and presented by the categories in the standard CRF groups and presented in the CTR as a frequency-distribution.

For categorical data, tabulations of frequencies will include all defined categories even if there is no count in a category. Tabulations of frequencies will display the number of observations in a category as well as the percentage (%) relative to the number of subjects in the respective treatment group. All patients in the respective patient set are used whether they have non-missing values or not, unless otherwise specified. Percentages will be rounded to one decimal place. The category missing will be displayed only if there are missing values.

If applicable, conversion from days to weeks, months and years will be as follows:

- weeks = days ÷ 7
- months = 12 × days ÷ 365.25
- years = days ÷ 365.25.

### **7.1 DEMOGRAPHIC AND OTHER BASELINE CHARACTERISTICS**

Only descriptive statistics and summary tables are planned for this section of the report. Data will be summarised by treatment group and a "total" column will be included in the summary table.

### **7.2 CONCOMITANT DISEASES AND MEDICATION**

Only descriptive statistics are planned for this section of the report.

Concomitant diseases (i.e., baseline conditions) will be coded similarly as AEs using the most recent version of MedDRA. A summary of concomitant diseases will be provided by

treatment group, System Organ Class (SOC) and Preferred Term (PT). Concomitant diseases which are present at start of the study will be descriptively summarized by treatment. A medication/therapy will be considered concomitant to treatment if it (1) is ongoing at the start of randomized trial treatment or (2) starts within the on-treatment period (see [Section 6.1](#) for a definition of study analysis phases). A medication/therapy will be considered as prior medication/therapy, if the end date of the medication/therapy is at any time prior to the start of randomized trial treatment.

Concomitant therapies (CTs) are coded according to WHO Drug Dictionary. CTs will be classified according to the Anatomical, Therapeutic, Chemical (ATC) classification system. The third ATC level will be used to categorize CTs by therapy type. In situations where a medical product may be used for more than one equally important indication, there are often several classification alternatives. As appropriate, subjects receiving CTs with more than one possible ATC level-three category will be counted more than once and footnote will clarify this possible multiple counting in tables. The most current MedDRA and WHO DD versions will be used.

